#### 5.4.2. Venetoclax Administration

If a dose is missed or vomited, the next dose should not be increased to account for missing a dose. The subject should take the next regular dose at the regularly scheduled time.

Day 1 of each cycle will be counted from the start of the azacitidine infusion. Treatment may be prolonged beyond the planned 28 days of each cycle if the start of the next course of azacitidine is delayed. However, if there are adverse events that mandate treatment interruption or it is considered in the best interest of the subject for safety reasons to interrupt DS-1594b and/or venetoclax therapy, DS-1594b and/or venetoclax administration can be transiently discontinued and re-started as per guidelines in Section 6.

### 5.5. Phase 2 Cohort D: R/R ALL treated with miniHCVD with DS-1594b

Subjects will be treated according to the following dose levels:

**Table 7: Dose levels for miniHCVD, and DS-1594b**

Dose Level	miniHCVD	DS-1594b
-1	As published  miniHCVD regimen	Lower dose of DS-1594b as recommended by SRC
0 (Starting dose)	As published miniHCVD regimen	One dose level below the RP2D of DS-1594b from the Phase 1
1	Not applicable	RP2D of DS-1594b from the Phase 1

DS-1594b orally twice daily (or daily, dependent on results from dose escalation phase). In each cycle, DS-1594b will be taken daily continuously.

Variations in dose reductions of the individual chemotherapy or the administration of venetoclax or supportive care dose schedules other than those suggested below are allowed in the best interest of subjects. Such subjects should be discussed with the principal investigator. Dose escalations of chemotherapy above those outlined in the protocol; however, are not allowed. Variations in infusion times due to minor differences in IV bag overfill/underfill and institutional procedure on flushing chemotherapy lines will not result in protocol deviation.

#### 5.5.1. Treatment Overview

DS-1594b will be given orally twice daily (or daily, dependent on results from dose escalation phase) in combination with mini-hyper-CVD. Each cycle is 28 days. Mini-hyper-CVD chemotherapy regimen consists of a total of 8 cycles of intensive chemotherapy with Mini-hyper-CVD alternating with high-dose methotrexate and cytarabine administered approximately every 28 days (or later to allow for recovery from myelosuppression or infection). Subjects will then receive up to 2 years of maintenance with: DS-1594b, vincristine and corticosteroids.

Subjects who are responding, and without any major drug-related toxicity, may continue DS-1594b until the end of the 2-year maintenance period.

**Cycle 1:** Eligible subjects will receive DS-1594b orally twice daily (or daily) in the in-patient setting in combination with Mini-hyper-CVD chemotherapy starting together on Day 1. The subjects will remain hospitalized up until the completion of chemotherapy. The hospital stay may be prolonged in subjects with infections or other issues requiring an in-patient stay. The remainder of the course of DS-1594b can be administered as an out-patient. Dose level 0 is the starting dose level and will be one dose level below the RP2D, and dose level -1 will only be explored if there is excess toxicity with the starting dose. If dose level 0 is tolerated, escalation to the RP2D will be performed as described in Section 3.3. Each cycle is 28 days, however additional days may be needed for subject recovery before starting the next cycle. At the end of Cycle 1, subjects will have bone marrow aspirate/biopsy for response assessment.

Hydroxyurea and/or dexamethasone is allowed prior to the beginning of Mini-hyper-CVD.

**Cycles 2 – 8:** Subjects will continue DS-1594b orally twice daily (or daily) continuously. Chemotherapy from the mini-hyper-CVD regimen will be administered in the in-patient setting, starting on Day 1 of each of the Cycles 2 through 8. The subjects may remain hospitalized up until the completion of chemotherapy. Hospital stay may be prolonged for subjects with infections or other issues requiring in-patient stay. The remainder of the course of DS-1594b can be administered as an out-patient.

Upon completion of the 8 courses of the Mini-hyper-CVD regimen, subjects may continue DS-1594b orally twice daily (or daily) continuously of each 28-day cycle for up to 2 years during maintenance. The dose will be according to the dose level administered during Cycles 2 through 8. Subjects may be moved from the intensive chemotherapy phase to the maintenance phase with vincristine, steroids, DS-1594b orally twice daily (or daily) continuously prior to completion of 8 cycles of chemotherapy due to frequent infectious complications, or if the subject is intolerant to the chemotherapy (after discussion with the Principal Investigator). If an early transition to maintenance phase is planned, subjects should receive at least 2 cycles of intensive chemotherapy. The reason for early transition to the maintenance phase must be documented in the medical record.

At any time while enrolled in this trial, subjects may be referred for hematopoietic stem cell transplantation at the discretion of the treating physician. DS-1594b will be discontinued at least 2 days prior to the start of the conditioning regimen for hematopoietic stem cell transplantation.

### **5.5.2. Mini-Hyper-CVD Regimen**

#### **5.5.2.1. General Considerations**

- The Mini-hyper-CVD (odd cycles) will alternate with methotrexate and cytarabine (even courses) administered on Day 28 (if count recovery allows) or later day cycle (as count recovery allows).
- Anti-emetic therapy with each course of intensive chemotherapy as needed.

- Filgrastim (G-CSF) will be administered with each course after the completion of chemotherapy. Peg-filgrastim may replace filgrastim (G-CSF). Biosimilars may be used for filgrastim or peg-filgrastim.
- Next cycle may be started when granulocytes  $> 1.0 \times 10^9/L$  and platelets  $\geq 50 \times 10^9/L$ . Cycles may be started with dose reductions prior to full platelet recovery, if the treatment is delayed (e.g., greater than 28 days from last cycle).
- Prophylactic antibiotics may be given with each course until neutrophil recovery to  $0.5 \times 10^9/L$  or greater (or other antibiotics if being treated for active infection). Suggestions include: Levaquin 500 mg orally daily; trimethoprim-sulfamethoxazole double-strength one tablet orally twice daily; or other appropriate antibacterial agent. Caspofungin or another appropriate antifungal agent. Valacyclovir 500 mg orally daily; or acyclovir 200 mg orally twice daily; or another appropriate antiviral agent.
- Omit azoles on Day -1, same day, and day after vincristine.
- In general, 8 cycles of chemotherapy (4 Mini-hyper-CVAD, 4 methotrexate plus cytarabine) will be administered in approximately 28-day intervals (depending on the recovery of blood counts). Thereafter, maintenance therapy with DS-1594b in combination with, vincristine and corticosteroids may be continued for up to 2 years of maintenance. Modifications thought to be in the best interest of the subject are allowed after discussion with the Principal Investigator. Subjects will be followed indefinitely for relapse and survival.
- For subjects with CD20 expression ( $\geq 20\%$  by flow cytometry) Rituximab 375 mg/m^2 may be added on Days 1 ( $\pm 3$  days) and 11 ( $\pm 3$  days) of Cycles 1 and 3, and on Days 1 ( $\pm 3$  days) and 8 ( $\pm 3$  days) of Cycles 2 and 4. For subjects receiving rituximab all therapy can be moved back 1 day if needed (i.e. Day 1 starts Day 2, Day 2 starts Day 3, etc.).
- Methotrexate dose regimen will be adjusted as indicated below for pleural effusions.

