- i. Known dysphagia, short-gut syndrome, gastroparesis, or other conditions that limit the ingestion or gastrointestinal absorption of drugs administered orally
- j. Known history of testing positive for HIV or known acquired immunodeficiency syndrome (test at screening only if required by local regulations)
- k. Known history of Hepatitis B virus (HBV) or hepatitis C virus (HCV) infection with active Hepatitis B or C infection at screening (positive HBV surface antigen or HCV RNA if anti-HCV antibody screening test positive)
- l. Vaccination with live-attenuated vaccines within 4 weeks of the first dose of study drug and while on trials is prohibited (COVID-19 vaccination is permitted)
- m. Subjects who are currently receiving treatment with medication that meet one of the following criteria and that cannot be discontinued at least one week prior to the start of DS-1594b treatment:
  - Medications that may prolong QTc interval and have a known risk of inducing Torsades de Pointes unless it is vital for the care of the subjects (see Appendix [Table 28](#)[Table 29](#))
  - Strong inhibitors or inducers of CYP3A (see Appendix [Table 29](#)[Table 29](#))
  - CYP3A and CYP2C19 substrates with narrow therapeutic index (see Appendix [Table 29](#)[Table 29](#))
- n. Subjects who consume grapefruit products, Seville oranges, or Star fruit within 3 days prior to the first DS-1594b administration and until the last day of DS-1594b is completed.
- o. **Additional exclusion criteria for the DDI sub-study and food effect sub-study (see Appendix [Table 31](#)[Table 34](#))**
  - Subjects who are currently receiving moderate inhibitors or inducers of CYP3A who cannot discontinue at least one week prior to the start of DS-1594b treatment till the end of sub-study period (note that strong CYP3A inhibitors or inducers still need to be restricted as defined in Section [4.2m](#)).
  - Subjects who are currently receiving proton pump inhibitors who cannot discontinue at least 2 days prior to the start of DS-1594b treatment till the end of sub-study period.

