## 5.3. Phase 2 Cohort B: R/R AML with NPM1 mutation

### 5.3.1. Dose Administration Guidance

The general dose administration guidance for DS-1594b as listed in Section 5.1 should be followed.

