#### **5.6.2. Medications that may prolong the QTc interval**

Medications that may prolong QTc interval and have a known risk of inducing Torsades de Pointes should be avoided unless it is vital for the care of the subjects:

- Concomitant use of DS-1594b with drugs known to have a high risk of increasing the QTc interval, and drugs known to increase the QTc interval that are also primarily metabolized by CYP3A should be avoided. See Appendix [Table 28](#)[Table 28](#).

Formatted: C-Hyperlink

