**Table 9: Recommendations for the use of concomitant medications and therapies**

Category of Use	Medication	Comment on Use	Restriction on Use
Recommended	Prophylactic antibiotics, antifungal agents, and antiviral agents	Strongly encouraged	Refer to Appendix Table 22 Table 22 , Table 23 Table 23 , Table 25 Table 25 for restrictions, and Section 5.3.
	Antiemetic agents	According to standard of care at the site	Avoid QTc prolonging antiemetics (Section 10)
Allowed	Oral allopurinol or rasburicase	According to standard of care at the site	None
	Leukapheresis	According to standard of care at the site	Before first dose on Day 1 = 1 only
	Red blood cell transfusion	None	None
	Platelet transfusion	None	None
	White blood cell transfusion	At Investigators discretion according to standard of care at the site	None
	Myeloid growth factors or platelet growth factor	At Investigators discretion according to standard of care at the site	None
	Erythropoietin or darbepoetin	At Investigators discretion according to standard of care at the site	None
	Any other medication for supportive care	At Investigators discretion according to standard of care at the site	None

Consistent with subject safety and comfort, administration of any prescription or over-the-counter drug products other than study medication should be minimized during the study period. Subjects should be discouraged from use of street drugs, herbal remedies, self-prescribed drugs, tobacco products, or excessive alcohol during the clinical study.

If considered necessary for the subject's wellbeing, drugs for concomitant medical conditions or for symptom management may be given at the discretion of the investigator. The investigator's decision to authorize the use of any drug other than study drug should take into account subject safety, the medical need, the potential for drug interactions, the possibility for masking symptoms of a more significant underlying event, and whether use of the drug will compromise the outcome or integrity of the study.

Subjects should be instructed about the importance of the need to inform the clinic staff of the use of any drugs or remedies (whether prescribed, over-the- counter, or illicit) before and during the study.

Recommendations for specific types of concomitant therapies, supportive care; diet and other interventions are as follows:

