**Table 22: Stopping Boundaries for Toxicity and Futility Monitoring in Each of Cohorts A-D**

	Toxicity Stopping Boundaries		Futility Early Stopping Boundaries	
Number of Subjects (inclusive)	Num DLTs (inclusive) are considered too toxic	Actions for toxicity monitoring	Num. Responses (inclusive) are considered futile	Actions for futility monitoring
10	4 - 10	Early stopping	0 - 1	Early stopping
15	5 - 15	Early stopping	0 - 2	Early stopping
20	6 - 20	Early stopping	0 - 4	Early stopping
26	8 - 26	Reach to Nmax	0 - 6	Reach to Nmax

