## 10. APPENDICES

**Table 28: List of Prohibited QT Prolongation Drugs**

Prohibited medications causing QTc prolongation			
Antiarrhythmic:	Anticancer:	Antibiotic:	Antianginal:
amiodarone	arsenic trioxide	azithromycin	bepridil
disopyramide	vandetanib	clarithromycin*	
dofetilide	oxaliplatin	erythromycin*	Antipsychotic:
flecainide	Antihistamine:	moxifloxacin	chlorpromazine
ibutilide	astemizole*	sparfloxacin	haloperidol*
procainamide	terfenadine*	levofloxacin	mesoridazine
quinidine*		ciprofloxacin	pimozide
sotalol	Antimalarial:	grepafloxacin	thioridazine
dronedarone*	chloroquine	Antinausea:	sulpiride
	halofantrine	domperidone	levomepromazine
Antilipemic:	hydroxychloroquine	droperidol	Opiate agonist:
probucol		ondansetron	levomethadyl
Antidepressant:		GI stimulant:	methadone
citalopram	Anti-infective:	cisapride*	cocaine
escitalopram	pentamidine		Other:
			anagrelide
			sevoflurane
			cilostazol
			donepezil
			papaverine
			propofol

Note: \*CYP3A substrate

Source: The most updated list is available on website <https://www.crediblemeds.org/healthcare-providers/drug-list>

**Table 29: Prohibited Medications That Are Strong Inhibitors or Inducers of CYP3A, or CYP3A/P-Gp and CYP2C19 Substrates with Narrow Therapeutic Indices**

CYP3A4/5 substrates and/or P-gp substrates with narrow therapeutic index			
astemizole*	diergotamine	pimozide*	alfentanil
cisapride*	ergotamine	quinidine*	terfenadine*
cyclosporine	fentanyl	tacrolimus	sirolimus
digoxin	paclitaxel		
CYP2C19 substrates with narrow therapeutic index			
(S)-mephénytoin			
Strong CYP3A inhibitors			
Macrolide antibiotics:	Antivirals:	Antifungals:	Others:
clarithromycin**	indinavir	itraconazole**	conivaptan
telithromycin	lopinavir/ritonavir	ketoconazole	
troleandomycin	nelfinavir	posaconazole	mibefradil
	ritonavir**	voriconazole	nefazodone
	indinavir/ritonavir**		
	saquinavir		
	saquinavir/ritonavir**		
	telaprevir**		
	tipranavir/ritonavir**		
	danoprevir/ritonavir**		
	elvitegravir/ritonavir**		
	boceprevir		
	cobicistat		
Strong CYP3A/5 inducers			
avasimibe	carbamazepine	phenobarbital	phenytoin
rifabutin	rifampin	St. John's wort	mitotane

\* Compounds known to increase QTc interval that are also primarily metabolized by CYP3A4/5.

\*\* Compounds known to have P-gp inhibitory effect

Reference:

University of Washington's Drug Interaction Database

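### Section 5.5.2.1 suggests levofloxacin as optional prophylaxis in Cohort D, although Table 28 prohibits it and Section 5.6.2 says to avoid such drugs unless vital

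*Combined protocol and SAP*

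**What the plan says.** Section 5.5.2.1 allows prophylactic antibiotics with each Cohort D chemotherapy course until neutrophils recover. For the antibacterial it writes "Suggestions include: Levaquin 500 mg orally daily", then names trimethoprim-sulfamethoxazole, then leaves room for any other suitable agent. It mentions neither QTc nor Table 28.

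The appendix contains "Table 28: List of Prohibited QT Prolongation Drugs", and levofloxacin is in its antibiotic column. Section 5.6.2 is the operative rule: drugs that may prolong QTc and have a known risk of torsades "should be avoided unless it is vital for the care of the subjects", with a reference to Table 28. Exclusion criterion m in Section 4.2 applies the same limit at entry. It excludes subjects on such a drug that "cannot be discontinued at least one week prior to the start of DS-1594b treatment", again unless the drug is vital.

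Table 9 in Section 5.6.5 has a row for "Prophylactic antibiotics, antifungal agents, and antiviral agents". It strongly encourages their use and, for restrictions, sends the reader to Tables 22, 23 and 25 and to Section 5.3. The antiemetic row of the same table gives the QT restriction directly: "Avoid QTc prolonging antiemetics (Section 10". The text below Table 9 has a bullet on anti-infectives, which bars those listed in Table 29 (the CYP3A list).

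**The concern.** A clinician who takes the first suggestion in the Cohort D treatment section gives a drug that the protocol elsewhere tells sites to avoid. The setting makes this matter. Section 2.4.2 reports potent hERG activity for DS-1594b (IC50 0.3 µM) and QTc prolongation in monkeys, and Section 2.4.3 lists QT prolongation among the potential risks.

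Two things are at stake. The first is avoidable exposure of Cohort D subjects to a second QT-prolonging drug. The second is attribution. Grade 3 QTcF prolongation is a dose-limiting toxicity (DLT) criterion in Section 3.2.2, but an event counts only if it is judged unrelated to concomitant medication. Levofloxacin would give any QTcF event in the DLT window a second plausible cause.

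**Working it through.** There is no figure to reproduce, so the check is a side-by-side reading.

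1. **Same drug.** Section 5.5.2.1 uses the brand name and Table 28 the generic name. That Levaquin is levofloxacin is the one fact taken from outside the documents.

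2. **Same time.** The text under Table 7 (Section 5.5) has DS-1594b taken continuously in every cycle. Prophylaxis under Section 5.5.2.1 runs with each course until the neutrophil count reaches 0.5 × 10⁹/L. The two drugs would therefore overlap.

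3. **Does an exception apply?** Section 5.6.2 and exclusion m make an exception for a vital drug. Section 5.6.5 lets a subject continue on a prohibited drug that is essential, with principal investigator (PI) and sponsor approval. The prophylaxis in Section 5.5.2.1 is optional and has a named alternative, so as written it meets neither condition. No text exempts Cohort D from Table 28.

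4. **Does the antibiotic-specific text lead a site to Table 28?**
   - Table 9, antibiotic row. In this version Table 22 is "Table 22: Stopping Boundaries for Toxicity and Futility Monitoring in Each of Cohorts A-D", Tables 23 and 25 give operating characteristics and early-stopping probabilities, and Section 5.3 is "5.3. Phase 2 Cohort B: R/R AML with NPM1 mutation". None is a drug list. The numbering looks stale: 22 + 6 = 28, 23 + 6 = 29 and 25 + 6 = 31, which are the QT list, the CYP3A list and the sub-study list. This is an inference, and the shift does not explain the Section 5.3 reference; concomitant medication is now in Section 5.6.
   - Section 5.6.5, anti-infective bullet. It refers only to Table 29, and levofloxacin is not in Table 29.

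5. **What could it change?** Section 5.5.2.1 applies to Cohort D alone, so selection of the maximum tolerated dose in Phase 1 is untouched. Within Cohort D, QTcF DLTs are counted over the first 28 days. The run-in decision in Section 3.3 turns on at most 1 versus at least 2 DLTs in 6 subjects, so how one event is attributed can decide it. The toxicity boundary in Table 22 also counts DLTs (4 or more in the first 10). QTcF events after the window affect subject safety and dosing but not these counts.

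**The case against.** The strongest reply is that the protocol already settles the matter. Section 5.6.1 permits supportive medication subject to the exceptions that follow it. Section 5.6.2 is one of those exceptions and applies to every cohort, and Section 5.6.5 asks the investigator to weigh drug interactions before authorizing any other drug. Section 5.5.2.1 is a non-binding list, and a site complies simply by choosing another agent. The word prohibited comes from Table 28; the operative text is the softer rule of avoiding the drug unless vital. All of this stands. It shows which text prevails, but it does not make the two texts agree.

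The controls are also substantial. Entry requires QTcF no higher than 450 msec. Table 21 schedules triplicate ECGs on Days 1, 8 and 15 of Cycle 1 and on Day 1 of Cycles 2 to 6, and Section 8.5 has them read centrally. Table 12 requires DS-1594b to be reduced or interrupted by QTcF grade. Cohort D subjects start Cycle 1 in hospital, and the Safety Review Committee (SRC) sees ECG data before expansion. These reduce the risk. They act mostly by detecting prolongation, however, and after Cycle 6 Table 21 requires an ECG only if clinically indicated, while the regimen has 8 courses.

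A reader might infer from the Section 5.6.5 bullet that QT-prolonging antibiotics are largely uncontrolled. The documents do not support that: the bullet is a CYP3A rule, and QT control sits in Section 5.6.2 and Table 28. Nor should the Table 9 references be read as several independent failures. The three table numbers fit a single renumbering slip, and the row was probably meant to lead to Table 28.

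**Conclusion.** The plan is wrong as written: an internal inconsistency with a patient-safety consequence. Section 5.5.2.1 suggests a drug that Table 28 prohibits and that Section 5.6.2 says to avoid unless vital. It carries no caveat, and the Table 9 row that should redirect the site does not do so as printed. The change should be made, although the general rule already governs. Confidence is high, because the conclusion rests only on the text and on Levaquin being levofloxacin.

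The size cannot be stated as a QTcF shift or a change in DLT counts, because the documents give no levofloxacin effect and no expected uptake of the suggestion. A reader might assume that the whole cohort is exposed throughout all courses, or that DLT counts are distorted throughout treatment. Neither follows: use is optional, it stops at neutrophil recovery, and the attribution concern is confined to the 28-day DLT window in Cohort D. No sample size, stopping boundary or analysis is affected.

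**What to change.** - **Section 5.5.2.1:** delete Levaquin, or make it explicitly subject to Section 5.6.2 and to the PI and sponsor approval in Section 5.6.5. End the antibacterial list with *other appropriate antibacterial agent not listed in Table 28 or 29*. Naming ciprofloxacin or moxifloxacin instead would not help, since both are in Table 28.
- **Table 9, antibiotic row:** replace the present references with Tables 28, 29 and 31 (the last for the sub-studies) and Sections 5.6.2 and 5.6.4. Add an instruction to avoid QTc-prolonging agents, matching the antiemetic row.
- **Section 5.6.5, anti-infective bullet:** add a reference to Section 5.6.2 and Table 28 beside Table 29.

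The cost is three wording edits, best made before Cohort D opens, with no change to data collection or analysis. The downside is one fewer named prophylaxis option: if Levaquin is deleted, trimethoprim-sulfamethoxazole is the only antibacterial named, with other suitable agents still allowed and levofloxacin still available through the existing exceptions.
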